1.3 REVIEW OF RELEVANT EXISTING EVIDENCE

As noted above recent SRs and meta-analyses (MAs) conclude that overall effects on *mortality* are similar between restrictive and liberal RBC transfusion strategies²⁶ ³⁵, but no studies were conducted specifically in our study population. Importantly, heterogeneity of effects are emerging from recent SRs/MAs restricted to populations with co-morbidities²⁷ ²⁸. Two ICU based transfusion trials measured HRQoL: a trial in septic shock patients³⁶, and our trial in older patients requiring prolonged mechanical ventilation³⁷. The intervention in both trials occurred during ICU, and ICU mortality was high. Survivor cohorts were small, confirmed markedly reduced HRQoL, but found no differences in HRQoL. In addition to limited statistical power, these analyses did not adjust for baseline health status or other factors, which we and others have shown to be important determinants of HRQoL in heterogeneous ICU populations³⁸ ³⁹. No rehabilitation trials have considered anaemia treatment either as the main intervention or as part of the intervention.²³

A large observational literature demonstrates the high disability burden suffered by ICU survivors, especially during the first 3-6 months, but often lasting many years. This includes physical impairments, reduced Activities of Daily Living (ADLs), and mental and cognitive disability. ^{1 3 40} Pre-existing health status is an important determinant of post-ICU disability, but has not been widely considered in published trials, which may explain in part why the increasing number of ICU rehabilitation trials have demonstrated disappointing effects on outcomes.

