9 STATISTICS AND DATA ANALYSIS

9.1 SAMPLE SIZE CALCULATION

Based on our previous research^{2 18} we estimated mean PCS SF-36 at 90 days will be significantly reduced at 35-40 (normal population average value 50), with standard deviation (SD) of 10-15 points. We defined a minimum clinically important difference as 5 points of the PCS element of the SF-36 at 90 days (smaller differences are of unlikely importance to patients)⁴¹. This represents an effect size of 0.42. Assuming the mean (SD) PCS will be 38 (SD 12) with restrictive (usual) care, to detect an improvement from RBC transfusion to a mean PCS of 43 at 90% power (two-sided P value 0.05) would require 244 patients.

In this population there is a risk of loss to follow-up (other than death), which in most previous trials has been between 10% and 30%. We originally proposed to inflate the sample size allowing for a 20% loss to follow-up at 90 days. This required a sample size of 305 (randomised 1:1 between the two groups). Adjusting for pre-specified baseline covariates is expected to further increase study power and/or protect against extra variability.

In May 2024, follow-up completion for the primary outcome was 75% despite active attempts to maximise this. As part of the strategy to ensure internal validity and adequate study power it was agreed to increase the sample size to ensure complete follow-up for at least 244 surviving patients. Rates of deaths during follow-up were

12/182 (7%). A conservative approach was agreed, assuming loss to follow-up might be as high as 30%. This required an inflation in sample size from 305 to 346 patients to ensure at least 90% power for a difference in the SF-36 PCS of 5 points.

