Secondary outcomes: Secondary outcomes will be analysed using models appropriate for the type of outcome (e.g. for continuous outcomes as per the primary endpoint/principal analysis; mortality using a Cox proportional hazards model, binary outcomes with adjusted logistic regressions).

9.2.1 Health Economic Evaluation:

The cost-effectiveness of the intervention compared with 'usual care' will take the format of a within-trial cost-effectiveness analysis and use a cost-utility analysis framework. The primary health economic outcome measure will be the incremental cost per QALY at 180 days, and a further analysis will assess the cost per LYR at 180 days. In addition, the impact of the intervention on the downstream costs, health outcomes and cost effectiveness will we assessed over a 5-year time period (depending on the results of the shorter term trial main outcome analyses). The perspective for analysis will be that of the NHS budget holder, with a secondary analysis taking a wider societal perspective (e.g. including indirect costs in terms of the costs of lost productivity).

Estimation of health service costs will rely on a combination of scrutinisation of medical records by the research team, patient completed questionnaires and linkage to routinely collected administrative healthcare data (the decision on the latter approach will be determined based on the results of the main trial and any effects seen). This will include Hospital Episode Statistics (HES) in England and the Scottish Morbidity Record (SMR), Patient Level Costing and Information System (PLICS), the Prescribing Information System (PIS) and the Unscheduled care DataMart in Scotland to include, inpatient, outpatient, A&E, community prescribing and unscheduled care. This efficient strategy will limit missing data and accurately reflect real-world activity. Unit costs for all resources used will be obtained from routine published UK/national sources (e.g. NHS Reference Costs, the Personal Social Services Research Unit).

Assessment of quality of life (health-related utility) for the estimation of QALYs will rely on the SF-6D derived from the SF36. Longitudinal utility will be adjusted for baseline values.

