To summarise the analysis will present the Incremental Cost-effectiveness Ratio (ICER), the Scatterplot on the Cost-effectiveness Plane and the Cost-effectiveness Acceptability Curve (to show the probability that the intervention is cost-effective for different values of willingness to pay per additional QALY). Moderation analysis will

reflect the main statistical analysis and multivariable analysis of cost outcomes will rely on generalised linear models. Uncertainty will be estimated using non-parametric bootstrapping (for calculating the confidence intervals around cost per QALY ratios, using bootstrapped estimates of the mean cost and QALY differences). Missing data will be handled as considered most appropriate at the time of analysis, likely using multiple imputation.

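### The protocol plans a bootstrap confidence interval on the cost-per-QALY ratio and gives no alternative if the QALY difference is not clearly different from zero, when that interval cannot be interpreted (minor)

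*Protocol*

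**What the plan says.** Protocol section 9.2.1 (Health Economic Evaluation) sets the outcome: "The primary health economic outcome measure will be the incremental cost per QALY at 180 days". QALYs "will rely on the SF-6D derived from the SF36. Longitudinal utility will be adjusted for baseline values".

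For uncertainty, the same section plans non-parametric bootstrapping "for calculating the confidence intervals around cost per QALY ratios", built from replicates of the mean differences in cost and in QALYs. It also plans "the Scatterplot on the Cost-effectiveness Plane and the Cost-effectiveness Acceptability Curve", the latter "to show the probability that the intervention is cost-effective for different values of willingness to pay per additional QALY".

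The section does not mention net monetary benefit or separate intervals for the cost and QALY differences. It gives no rule for replicates whose QALY difference is zero or negative. It also does not say which type of bootstrap interval will be used.

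**The concern.** The ICER is the mean cost difference divided by the mean QALY difference. As the denominator passes through zero, the ratio jumps between large positive and large negative values. Its sign is also ambiguous:

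- A negative ratio means the intervention is cheaper and better (dominant) in one quadrant of the cost-effectiveness plane, and dearer and worse (dominated) in the opposite one.
- A positive ratio means either dearer and better, or cheaper and worse.

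Once replicates spread over several quadrants, the ordering of the raw ratios no longer matches an ordering of preference. Limits on that scale then have no decision meaning.

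The condition is realistic here. The horizon is short: 180 days is 0.493 years, so a gain of 0.02 QALY needs a mean utility gain of 0.02 / 0.493 = 0.041 held throughout. The trial is sized on the SF-36 PCS, not on QALYs. Section 1.3 says of the two earlier ICU transfusion trials that measured quality of life: "Survivor cohorts were small, confirmed markedly reduced HRQoL, but found no differences in HRQoL". At stake is the interval reported with the primary health economic result.

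**Working it through.** **Sample size available.** Section 9.1 uses a 5-point PCS difference, with usual care described as follows: "Assuming the mean (SD) PCS will be 38 (SD 12) with restrictive (usual) care". At 90% power and two-sided 0.05:

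n per arm = 2 × 12² × (1.960 + 1.282)² / 5² = 121.05, rounded up to 122, so 244 in total. This reproduces the protocol's figure.

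With 346 randomised and 30% lost, 346 × 0.7 = 242, or 121 per arm. That number is used below.

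**Assumed inputs.** The documents give no QALY SD, cost SD, expected differences or willingness to pay. I assume a 180-day QALY SD of 0.05, 0.07 or 0.09 and a true gain of 0.005 to 0.029. The top value is the protocol's standardised PCS effect applied to the middle SD, 0.42 × 0.07 = 0.029. It is a benchmark only, because a PCS effect does not convert directly to QALYs.

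**How often replicates cross zero.** SE = SD × √(2/121), which is 0.0064, 0.0090 and 0.0116 for the three SDs. Under a normal approximation, more than 2.5% of a trial's replicates fall below zero when estimate / SE is below 1.96. The probability of that is Φ(1.96 − gain / SE). For example, with SD 0.07 and gain 0.01: Φ(1.96 − 1.11) = Φ(0.85) = 80%.

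| True QALY gain | SD 0.05 | SD 0.07 | SD 0.09 |
|---|---|---|---|
| 0.005 | 88.1% | 92.0% | 93.7% |
| 0.01 | 65.7% | 80.2% | 86.3% |
| 0.02 | 12.5% | 39.7% | 59.2% |
| 0.029 | 0.5% | 10.3% | 29.2% |

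If imputation effectively kept all 346 (173 per arm, an upper bound), the row for 0.01 becomes 54%, 74% and 82%. The 0.02 entry at SD 0.07 falls to 24%.

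**What the interval would look like.** Further assumptions: QALY SD 0.07, gain 0.01, cost SD 8,000, cost difference 600, cost and QALY independent, 121 per arm, willingness to pay 20,000 per QALY.

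- ICER = 600 / 0.01 = 60,000.
- A percentile interval on the ratio runs from roughly −0.84 million to +0.98 million.
- About 34% of replicates have a negative ratio. Of these, 72% are dominant and 28% dominated.
- Net monetary benefit = 20,000 × 0.01 − 600 = −400. Its SE is √((20,000 × 0.07)² + 8,000²) × √(2/121) = 1,044, so the 95% interval is about −2,450 to 1,650. It is finite, ordered and drawn from the same replicates.

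**Coverage.** In a simulation with the same SDs and cost difference (2,000 trials, 1,000 replicates each, true gains 0.005 to 0.02), nominal 95% percentile intervals on the ratio covered the true value in 97.2 to 98.6% of trials. Net monetary benefit intervals covered 93.9 to 95.1%.

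**The case against.** **The protocol names no percentile method.** This stands. A reader might infer that it prescribes sorting raw ratios and cutting at 2.5% and 97.5%, but it does not. It keeps the paired cost and QALY differences, which would also allow limits drawn on the plane or a rule for reporting dominance. Section 9.2 defers statistical detail to the SAP, and interval construction could belong there. What the protocol does fix is the target of the interval, namely the ratio. Any interval on the raw ratio meets the same discontinuity and quadrant ambiguity.

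**The plane and acceptability curve already show decision uncertainty.** This stands, and it limits the harm. Both remain valid across quadrants, and the curve is the probability that net monetary benefit exceeds zero at each willingness to pay. Neither repairs an interval printed beside the ICER.

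**The ratio interval does not under-cover.** This stands. Coverage of 97 to 98% is conservative. The interval is hard to read and can be very wide, but the simulation shows no excess of missed true values.

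**The size depends on assumed inputs.** This also stands. At a gain of 0.029 with SD 0.07, the problem arises in about 10% of trials. Baseline adjustment of utility and the multiple imputation that section 9.2.1 calls likely should both improve precision. If nearly every replicate has a clearly positive QALY difference, the ratio interval is usable. That cannot be known in advance, and no alternative is stated.

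**Conclusion.** The point holds as a minor one. Section 9.2.1 commits to an interval on a quantity that may have no usable interval, and says nothing about what to report then. How often this would occur depends on inputs the documents do not give. Under the assumptions shown, it is likely at a true gain of 0.01 QALY or less, uncertain at 0.02 and uncommon to moderate at 0.029.

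Two stronger readings are not supported. One is that zero-crossing replicates are to be expected whatever the effect; the table shows this is conditional on a small gain or a large SD. The other is that the uncertainty analysis as a whole is invalid; the ICER point estimate, the plane and the acceptability curve are unaffected. The clinical primary analysis and the sample size are also untouched.

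**What to change.** Reword the bootstrap sentence in section 9.2.1 along these lines:

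- The bootstrap replicates will give 95% confidence intervals for incremental cost, for incremental QALYs, and for incremental net monetary benefit at stated willingness-to-pay values.
- The ICER will be reported as a point estimate with the cost-effectiveness plane and the acceptability curve.
- An interval on the ratio will be reported only if essentially all replicates have a positive QALY difference, with the required share stated before the data are seen.

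The cost is wording only. The data, the replicates and the planned displays stay the same, and the net monetary benefit intervals need one extra line of computation per willingness-to-pay value.

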10 ADVERSE EVENTS

Adverse Event (AE) and Serious Adverse Event (SAE) reporting will follow the ACCORD SOP for non-CTIMP trials (CR006).

Transfusion Related Adverse Events or Reactions and Serious Transfusion Related Adverse Reactions will be recorded in accordance with the definitions of SHOT (Serious Hazards of Transfusion), revised December 2019. Imputability of any transfusion related AE, AR or SAE will also be assessed according to the definitions given within the SHOT guidance (see Appendix 1)

https://www.shotuk.org/wp-content/uploads/myimages/SHOT-Definitions-update-10.01.20-FINAL.pdf

10.1 Definitions

10.1.1 Adverse Event (AE)

Any untoward medical occurrence in a study participant, which does not necessarily have a causal relationship with the study intervention.

10.1.2 Adverse Reaction (AR)

Any untoward and unintended response that has occurred due to the intervention.

10.1.3 Transfusion Related Adverse Reaction (AR) or Event

Any untoward and unintended response to a transfused blood component.

10.1.4 Serious Adverse Event (SAE) or Serious Adverse Reaction (SAR) or Serious Transfusion Related Adverse Reaction

Any AE or AR or Adverse Transfusion Reaction or unexpected adverse transfusion reaction that:

- results in death of the study participant
- is life-threatening*
- requires inpatient hospitalisation or prolongation of existing inpatient
- hospitalisation
- results in persistent or significant disability or incapacity
- consists of a congenital anomaly or birth defect
- results in any other significant medical event not meeting the criteria above

* Life-threatening in the definition of an SAE or SAR refers to an event where the participant was at risk of death at the time of the event. It does not refer to an event which hypothetically might have caused death if it were more severe.

10.2 Identifying and Recording AEs and SAEs

10.2.1 AEs and SAEs that do not require reporting

Patients included in the trial will have recently experienced life-threatening illness complicated by multiple events and complications that fulfil the definition of AEs and SAEs. For many patients the risk of further complications and events continues into the post-ICU recovery period. These include, but are not restricted to, events such as new infections, worsening of the original condition causing critical illness, worsening organ failure, critical care readmission, and cardiorespiratory complications.

The judgement of the local research team and PI will determine which events should be reported as AEs and SAEs based on clinical judgement for each event.

The following complications are being collected within the trial, and do not require reporting unless the local research team consider this appropriate:

- Major Adverse Cardiovascular Events (MACE)
- Transfusion Related Adverse Reactions
- Infections
- Death

10.2.1.1 Assessment of Transfusion Reactions

As mentioned above, transfusion related reactions will be assessed in accordance with the definitions and imputability as set out by SHOT, but will also be recorded as an AE on the trial database. All Serious Transfusion Related Adverse Reactions will be recorded as part of the trial data collection process.

10.2.2 Duration of AE and SAE reporting

AE and SAE reporting will start from the time of randomisation in the trial. AEs and SAEs will only be reported during the intervention period, namely from enrolment until the time of hospital discharge. Important events that might constitute AEs and SAEs that may plausibly be associated with the intervention are being recorded as part of trial data collection during 180 days follow-up after hospital discharge.

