2.3.2 Secondary Endpoints/Outcomes

Patient centred outcomes:

- 1. Physical Component Score (PCS) of the SF-36 HRQoL questionnaire (and its four sub-domains) at 30 and 90 days post-randomisation.
- 2. Patient fatigue (Fatigue Severity Scale (FSS)) at 30, 90 and 180 days post-randomisation
- 3. Mental component score SF-36 (and its four sub-domains) at 30, 90 and 180 days post-randomisation.
- 4. Activities of Daily Living (ADLs) (WHODAS questionnaire⁴) at 90 days post-randomisation
- 5. Patients alive at 30, 90 and 180 days post-randomisation
- 6. Patients alive at 5 years post-randomisation derived from data linkage
- 7. Haemoglobin concentration at 30 days post-randomisation

Resource use and cost-effectiveness (based on data linkage and questionnaires):

- 8. Post-ICU length of hospital stay;
- 9. Care costs during 180 days post-randomisation.

- 10. Incremental cost per QALY at 180 days
- 11. Care costs derived from data linkage during 5 years post-randomisation (depending on results from shorter term outcome analysis)

Process and Safety outcomes:

- 12. Protocol compliance (during intervention index hospital stay)
- 13. Hb concentration (during index hospital stay)
- 14. RBC use (during 90 days follow up)
- 15. New Infections (during 90 days follow-up)
- 16. Transfusion-related adverse events (during 90 days follow-up)
- 17. Major adverse cardiovascular events (MACE; during 90 days follow-up)

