date) ¹	4. New Infections (defined as any clinically suspected or proven infection occurring after	or	
	randomisation requiring a new course of antibiotics)	In a clinical Research Facility	
(surviving patients)	5. Major Adverse Cardiac Events (MACE), comprising: any confirmed stroke, myocardial	or	
	infarction, or cardiovascular death	In the patients home or current	
	6. Transfusion-related adverse events	residence	
	Haemoglobin concentration	or	
		In a hospital ward	
	2. Blood samples for erythrogenesis and inflammatory markers (for patients providing		
	permission for this and where feasible to collect)	Follow up undertaken by local	
		investigator team	
	Health service utilisation questionnaire		
90 days post	Physical Component Score (PCS) of the SF-36	Follow up by postal questionnaire	
randomisation (±14	2. Mental Component Score (MCS) of the SF-36	followed by telephone consultation	
days)¹		if required	
	4. WHODAS ADLs questionnaire		
(surviving patients)	5. New Infections (defined as any clinically suspected or proven infection occurring after		
	, ,	consulting electronic health record	
	6. Major Adverse Cardiac Events (MACE), comprising: any confirmed stroke, myocardial		
	infarction, or cardiovascular death		
		Follow up undertaken by local	
		investigator team	
	9. Health service utilisation questionnaire		

180 days pos		Follow up by postal questionnaire
randomisation (±14 days) ¹	, ,	followed by telephone consultation if required
uays).	4. Survival	ii required
(surviving patients)		Survival determined by local team consulting electronic health record
		Follow up by local investigator
5 years pos		team Five-year outcomes determined by
randomisation ²	Health care resource and costs (via data linkage)	data linkage without needing to contact patients.

¹ If follow up in person is not possible or feasible, or is declined by the patient, then research teams should make efforts to obtain questionnaire data either by postal questionnaire or via telephone.

² the decision to undertake data linkage will be determined based on the results of the main trial and any effects seen.

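### Section 10.2.2 relies on 180 days of post-discharge event recording that the endpoints and legible schedule do not provide for MACE, infections and transfusion-related events, and Table 1's survivor label leaves post-discharge cardiovascular deaths without assured classification

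*Protocol*

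**What the plan says.** Protocol section 10.2.2 sets the reporting period: "AEs and SAEs will only be reported during the intervention period, namely from enrolment until the time of hospital discharge". It then says that important events plausibly linked to the intervention are "being recorded as part of trial data collection during 180 days follow-up after hospital discharge".

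Section 10.2.1 names MACE, transfusion-related reactions, infections and death. It introduces them with "The following complications are being collected within the trial, and do" not need separate reporting unless the local team thinks it appropriate. Section 10.4 exempts the same events from expedited reporting to the sponsor.

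Section 2.3.2 gives the three non-death outcomes a shorter horizon: "New Infections (during 90 days follow-up"), "Transfusion-related adverse events (during 90 days follow-up") and "Major adverse cardiovascular events (MACE; during 90 days follow-up"). The Summary says the same. Survival is an outcome at 30, 90 and 180 days.

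Table 1 (section 6.2) marks its 30-, 90- and 180-day rows "surviving patients". In the 30- and 90-day rows it defines MACE as stroke, myocardial "infarction, or cardiovascular death". Section 7.3 collects MACE, including cardiovascular death, during the intervention without a survivor restriction; the intervention ends at acute hospital discharge (section 6.1.1). Section 6.2 also has sites confirm survival from local health records before contacting the participant at any follow-up.

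**The concern.** There are two separate problems.

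**Duration and clock.** Section 10.2.2 uses trial data collection as the reason why AE/SAE reporting can stop at discharge. For MACE, infections and transfusion-related events, that collection appears to end at day 90 after randomisation, not 180 days after discharge. These events are also exempt from separate reporting because the trial collects them. After discharge, trial data collection is therefore the only route laid down. If it stops at day 90, the section misdescribes the safety surveillance to sites, the ethics committee and the DMC.

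**Population.** A row limited to survivors cannot yield a cardiovascular death. A site that follows the label literally will omit cardiovascular deaths after discharge, and strokes, infarctions or infections between the last visit and death. A site that follows the MACE definition will look for them. A named secondary safety outcome could then be ascertained differently across sites, with the missing part tied to death. An analysis plan cannot recover data that sites were not told to collect, so this belongs in the protocol and case report form.

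**Working it through.** **Inputs**
- Discharge typically 2–3 weeks after randomisation (Summary, duration of intervention): day 14 to day 21.
- Outcome horizon for MACE, infections and transfusion-related events: day 90 (section 2.3.2). The 90-day visit window is ±14 days (section 6.2), so it closes at day 90 + 14 = 104.
- Horizon stated in 10.2.2: 180 days, counted from discharge.
- Deaths during follow-up 12/182, stated as 7%; planned sample 346 (section 9.1).

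**Step 1: the plan's own figures.** 12/182 = 0.0659, or 6.6%, which rounds to the stated 7%. The 180 days in 10.2.2 has no derivation to reproduce, so it is set against the endpoint list and schedule.

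**Step 2: what is collected, and to when**

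| Event | Section 2.3.2 | Legible in Table 1 | 180-day list in 6.2 |
|---|---|---|---|
| MACE | 90 days | 30- and 90-day rows | not listed |
| New infections | 90 days | 30- and 90-day rows | not listed |
| Transfusion-related events | 90 days | 30-day row | not listed |
| Death | 30, 90, 180 days | survival in the 180-day row | vital status check |
| Health service use | care costs to 180 days | 30- and 90-day rows | listed |

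Other than the SF-36 and fatigue questionnaires, only survival and health service use continue to day 180. Health service use may pick up some care, but it is not event recording. Parts of the 90- and 180-day rows of Table 1 are not legible in the text at hand, so the table is read together with 2.3.2 and 6.2.

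**Step 3: length of the uncovered period for the three events**
- End of the period claimed in 10.2.2: 14 + 180 = day 194, to 21 + 180 = day 201.
- Against the day-90 horizon: 194 − 90 = 104 days, to 201 − 90 = 111 days.
- Against the close of the 90-day window: 194 − 104 = 90 days, to 201 − 104 = 97 days.
- If 10.2.2 meant 180 days from randomisation: 180 − 90 = 90 days.

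For death, the 180-day check exists. The only mismatch is the clock, about 14–21 days.

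**Step 4: a death between discharge and day 90.** Take a patient discharged at 2–3 weeks and seen at the 30-day visit, who dies before the 90-day visit. Section 7.3 covers events to discharge. The 30-day visit covers events to that visit. The record check before the 90-day contact finds the death. No text tells the site to record the cause of death, or a stroke, infarction or infection between the 30-day visit and death, and the row heading points the other way.

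**Step 5: how many patients could be concerned.** 346 × 12/182 = 22.8, about 23 deaths. This is an upper figure for the second problem: deaths in hospital fall under 7.3, and deaths after day 90 lie outside the MACE horizon. The protocol does not give the split.

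**The case against.** The strongest case on the other side is that this is loose wording and that no data are lost.

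- **The label cannot be a literal filter.** The 180-day row carries it and still lists survival, taken from the electronic record. The label may govern patient contact only. That reading is reasonable, but nothing states it, and sites have to guess.
- **The lists in 6.2 are questionnaire completion orders.** The 90-day list also omits MACE and infections, although Table 1 collects them then. Absence from the 180-day list is therefore weak evidence alone, and the 180-day row is only partly legible. This stands, and it is why the point is limited to what is legible. The 90-day horizon in 2.3.2 and the Summary is explicit and does not depend on either list.
- **2.3.2 and Table 1 agree on duration.** Correct: for these three events, 10.2.2 is the section out of line.

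A reader might go further and infer that fatal events are lost. The documents do not support that. Deaths are ascertained from health records at 30, 90 and 180 days whether or not the patient can be contacted, and in-hospital cardiovascular death is collected for everyone. A reader might also infer that costs before death are lost; section 9.2.1 allows review of medical records and possible data linkage, so that does not follow. Nor is survival part of the hypothesis in 1.4.2; it is a research question in 1.4.1 and a secondary outcome.

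**Conclusion.** The point holds in limited form.

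First, 10.2.2 is inconsistent with 2.3.2 in duration and in clock start for MACE, new infections and transfusion-related events. The uncovered period is about 104–111 days as written, assuming the typical stay, or 90 days if counted from randomisation. This matters because the statement supports ending AE/SAE reporting at discharge.

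Second, the survivor label in Table 1 contradicts a MACE definition that includes cardiovascular death. Between discharge and day 90, the cardiovascular classification of deaths is not assured, and neither is the recording of non-fatal events between the last visit and death. At most about 23 patients are concerned, assuming that the 12/182 rate, whose follow-up length is not given, applies to all 346.

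It is tempting to turn this into a share of MACE missed. That would need the proportion of deaths after discharge, the proportion that are cardiovascular and the overall MACE rate. The protocol gives none of them, so no such figure is offered. The primary outcome and sample size are unaffected. The changes should be made because they are cheap and protect a named safety outcome.

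**What to change.** 1. In Table 1, limit the survivor label to questionnaires and blood samples.
2. State that MACE with cause of death, new infections and transfusion-related events are abstracted from the health record for all randomised patients, to day 90 after randomisation or death if earlier.
3. Reconcile the duration and clock start in 10.2.2 with 2.3.2, 6.2 and Table 1. Either bring 10.2.2 to the 90-day post-randomisation horizon for these three events, with death to day 180, or add the events to the 180-day record check.

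The cost is a wording and table amendment, with a matching case report form check, plus a small amount of record abstraction for patients who die (about 23 of 346 expected). Sites already consult these records to confirm vital status. Adding events to the 180-day check would cost more, because it means one further event review for every participant.
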